Purpose of the Study – The purpose of this study is to address the key question of whether and how family health history (FHH) is adopted as a tool to more efficiently manage patients at risk for breast, colon, ovarian, and hereditary cancer syndromes as well as thrombophilia and coronary heart disease (CHD) and to provide evidence supporting clinical utility -- improved health behaviors in patients and physician screening recommendations. Five health care delivery organizations will participate in this demonstration project: Duke University, the Medical College of Wisconsin, the Air Force, Essentia Health, and the University of North Texas Health Science Center. The study will take place in 'real world' clinical, socio-cultural, and demographically diverse (rural, underserved, academic, family medicine) clinics (n=34) in 5 states (CA, MN, NC, WI, TX) that include genomic medicine 'early adopter' and 'naïve' sites, as well as those that are EMR-enabled and others that are not, and will use a cluster randomized controlled pragmatic hybrid type III implementation-effectiveness observational study design. We anticipate enrolling **7000 English or Spanish speaking adult participants (at a minimum) over a 3-year period**; to reach this goal we need to enroll ~300 participants from each intervention clinic (assuming 10 of the 34 clinics will be dedicated controls). Specifically we will use Healthcare Effectiveness Data and Information Set (HEDIS) measures as intermediate clinical effectiveness measures for CHD and the selected cancers as well as survey/formative data and electronic medical record (EMR)

data as outcomes measures. The research model is purposely designed to mimic clinical delivery as an important step toward widespread implementation and sustainability. In addition we will use a cost-effectiveness analysis to compare usual care to the FHH guided preventive health model. **The completion of this project will result in an optimal strategy for integration of FHH data collection and clinical decision support (CDS) tools into an EMR and demonstrate the utility of the FHH intervention among diverse primary care patients, their settings, their providers, and the health systems that deliver their care.**

Specific Aim 1: To optimize the collection of patient entered FHH in diverse clinical environments for coronary heart disease, thrombosis, and selected cancers

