Participants will be enrolled through a central Duke research coordinator. Electronic consent, survey administration, FHH education and MeTree™ access will be web-based. They will have access to assistance for questions, but will view all educational resources electronically and collect and enter their own FHH from a computer, mobile device, or a dedicated clinic kiosk. After receipt of CDS output (pedigree, tabular FHH, and provider report for providers and pedigree and patient report for patients), the clinical encounter proceeds as usual. Participants may receive reports through a personal health record, patient

portal, email, or clinic printer, depending on the optimized process for each individual clinic setting.

Once enrolled, each participant will be provided an account to the electronic data capture system, through which the participant will first sign the electronic consent form. As of 04/08/2016 the study team has implemented and will continue to follow "Procedure for Updating Consent Documents.IT.SOP" located in the Full Protocol of the eIRB. , and then access the computer survey program and the MeTree family health history collection tool. For this process, they will electronically be provided education about how and what to collect for FHH; along with materials including brochures and a worksheet. In addition, they will be educated about the electronic surveys, electronic consent process, benefits and risks of study participation, how to use MeTree (the FHH collection tool), how to receive their CDS output, and who to talk to about questions. Each consented participant will then complete the baseline survey prior to the scheduled primary care provider visit. The baseline survey is re-administered with a request to the participant via email at 3 and 12 months to capture changes in health related activities, activation and risk perceptions. Patients or providers can communicate their desire to discontinue participation at any time to the study coordinator or the PI (figure 1).

Standard health behavior surveys (SF12 and PAM) will be used to collect data covering diet, exercise, knowledge, screening practices, activation, attitudes and perception of risk for cardiovascular disease and the study cancers, and family health history. Each subject will be assigned a Unique Study ID and only trained research staff will have access to the list of IDs and patient names, for the purpose of tracking surveys and collecting medical record data.

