Benefits: Two aspects of the study will provide information that will improve patient care in primary care: 1) Enhancing primary care physician decision making by the application of individualized evidence-based algorithms based on patient characteristics and 2) Enhancing patient decision making by using active patient facing tools to promote patient engagement and activation. Overall we anticipate greater patient and provider satisfaction and the potential for streamlined workflows with improved information exchange. Risk stratification with decision support can assist in decision making for both patients and providers by 1) increasing knowledge, 2) lowering uncertainty, 3) reducing the likelihood of indecision, and 4) increasing the match between decisions and values. These effects have both cognitive and emotional components that can influence “decisions” by shifting perceptions of: disease, disease risk, treatment, and treatment benefits. Patients are also given a copy of their pedigree which can be shared with and distributed among family members as well as retained by the patient as documentation of their effort to collect the family history and to share with other clinical providers involved in their care.

Costs to the Subject – There will be no costs to patients or providers for their participation, though it does require a small time commitment.

Data Analysis & Statistical Considerations – Effectiveness data will be summarized with descriptive statistics and plots. Generalized linear ordinal regression models (GLO)(the function `ordgelm` from the R statistics package) will fit ordinal survey outcomes to the continuous outcome variables. Associations will be considered significant when the regression coefficient is not zero; a false discovery rate of 5% will be used to correct

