for multiple comparisons. Multivariate analysis will control for clinic and provider. A p-value of <0.1 in stepwise regression will identify significant factors such as demographics, intent to change, and their interactions. The analyses for the multiple outcomes will follow the same procedure as the survey outcomes but using a logistic regression model that includes the 7 covariate factors (see sample size section). Although the study is implemented at the level of the clinical practice, the likelihood of clustering is low given that all participants undergo the intervention and the intervention is aimed at both the patient and the provider; however, to address the possibility of clustering, we will calculate a design effect; if it is 1 we will use standard tests and generalized linear mixed models with clinic and state as random effects, if not we will adjust the confidence intervals using a conditional logistic regression. Effect size bias is extremely unlikely in this study as all individuals within the clinics are offered the intervention, preventing the imbalance in treatment assignment that can lead to inaccurate point estimates.

ORCA survey data will be analyzed using this validated survey's scoring method. The results will be used to categorize institutions and/or the individual clinics according to their flexibility for adapting to new ideas/technologies, which will then be included as an explanatory variable in the analysis of the effectiveness data captured during the trial as well as to help understand barriers encountered during the implementation process.

Key Informant Interview data analysis will proceed with an initial review of the transcripts conducted independently by study investigators. Each coder will identify major thematic categories included in the *a priori* theoretical model and emergent categories. The coders will work together to develop a revised schema for content coding. Once the schema has been finalized, the coders will code the transcripts for relevant categories and have discussions that may lead to further revision and refinement of the code book. Findings from the pre-implementation interviews will be used to create a tailored implementation plan at each site.

As of 01/20/2017 [name] is no longer on key personnel for this protocol, however she has been added to outside key personnel and will assist with writing study publications. She will see data summaries only, and not individual data.

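### The patient survey is repeated at 0, 3 and 12 months to capture change, but the planned survey model states no term that would estimate change within a person

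*Combined protocol and SAP*

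**What the plan says.** Under Design & Procedures, each consented patient completes a baseline survey before the primary care visit. The same survey is then requested again "via email at 3 and 12 months to capture changes in health related activities, activation and risk perceptions". Under Purpose of the Study, the evidence sought for clinical utility is "improved health behaviors in patients and physician screening recommendations".

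Data Analysis & Statistical Considerations starts from description: "Effectiveness data will be summarized with descriptive statistics and plots". It then states that generalized linear ordinal regression "will fit ordinal survey outcomes to the continuous outcome variables", and associations are judged by whether the coefficient differs from zero, with a 5% false discovery rate. On adjustment: "Multivariate analysis will control for clinic and provider". On selection: "A p-value of <0.1 in stepwise regression will identify significant factors such as demographics, intent to change, and their interactions". The organizational-readiness (ORCA) category is added as an explanatory variable.

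On correlation, the section considers only the practice: "Although the study is implemented at the level of the clinical practice, the likelihood of clustering is low". If the calculated design effect is 1, it uses standard tests and "generalized linear mixed models with clinic and state as random effects". Otherwise it adjusts confidence intervals by conditional logistic regression.

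**The concern.** The survey is designed to show change in the same people, but the model written for it is a model of association. Nothing in it says how three answers from one person enter the analysis: which visit is the outcome, whether baseline is a covariate, or how a person's answers are allowed to correlate. The clinic and state effects deal with similarity between patients of one site, not between one patient's own answers.

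This matters because improved patient behavior is part of the stated purpose. Under Subject Recruitment and Compensation, patient invitations go out from intervention sites, and no survey of control-clinic patients is described. Change from baseline is therefore the main result the patient survey can give. As written, the choice of time point, baseline handling and correlation structure is left open until the data are in hand.

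**Working it through.** The plan gives no within-person correlation and no figure on this point to reproduce. The check is a comparison of sections, followed by arithmetic under an assumed correlation.

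**Step 1: what the design needs and what the model names.**

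- Needed for inference on change: a visit term, a paired comparison or a change score, with one person's answers allowed to correlate.
- Named for the survey model: clinic, provider, stepwise factors (demographics, intent to change and interactions, given as examples), the ORCA category, and random effects for clinic and state.
- Intent to change is a predictor, not measured change. No other section supplies a visit, participant, baseline or change term.
- The 7 covariates cited from a sample size section are attached to the separate logistic model for the other outcomes. That section is not in the text available for this review, so the covariates could not be checked.

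**Step 2: the two ways the model could be run.**

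- *Visit by visit.* Each person contributes one answer per model, so standard errors are not wrong for this reason. No coefficient estimates change, and the baseline answer is not used at follow-up.
- *Pooled.* Three answers per person are treated as independent. The plan does not say that this will be done.

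**Step 3: size.** Let ρ be the correlation between two answers from one person, assumed to be 0.4 to 0.6 and equal for all pairs of visits.

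Pooled, with m = 3 complete answers and a factor constant within a person: true SE ÷ reported SE = √(1 + (m − 1)ρ).

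Visit by visit, for a factor unrelated to baseline, on a linear scale: SE with baseline adjustment ÷ SE without = √(1 − ρ²).

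| ρ (assumed) | Pooled: √(1 + 2ρ) | Baseline adjustment: √(1 − ρ²) |
|---|---|---|
| 0.4 | √1.8 = 1.342 | √0.84 = 0.917 |
| 0.5 | √2.0 = 1.414 | √0.75 = 0.866 |
| 0.6 | √2.2 = 1.483 | √0.64 = 0.800 |

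The pooled factor shrinks with incomplete data. With two answers each it is √(1 + ρ), that is √1.4 = 1.183 to √1.6 = 1.265.

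For a visit contrast added to a pooled model, the error runs the other way. The true SE is √(1 − ρ) times the reported one, from √0.6 = 0.775 to √0.4 = 0.632, so a test of change would be conservative.

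**The case against.** The strongest reply is that nothing is excluded. The stepwise list is open, the continuous outcome variables are undefined and might be meant to include change, and descriptive summaries by visit are planned. All of that is true, and it is why the point is that no such term is stated, not that one is ruled out. A term that might enter through stepwise selection is still not a specified estimate of change. The conditional logistic branch does not fill the gap either: no stratum is named, and the context is clustering by practice.

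Several stronger readings are tempting, and the documents do not support them.

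- *The survey standard errors are wrong.* That follows only under pooling, which is not stated.
- *The p<0.1 rule would pass too many null factors.* Under pooling, a single test of one null factor at a nominal 10% would reject with probability 2(1 − Φ(1.645/k)): 22% for k = 1.342 and 27% for k = 1.483. The plan uses stepwise selection and a false discovery rate correction, so this is not the error rate of its procedure.
- *The study loses power.* The documents give no survey effect size, so no power figure can be stated. At least 7000 patients are planned. For an illustrative 0.2 SD difference between equal halves, ignoring clustering, z = 0.2 × √7000 ÷ 2 = 8.4, so power is near 100% with or without baseline adjustment. The gain is in precision.
- *Change from baseline would show that the intervention works.* Without a surveyed control group, change mixes any effect with time trend, repeat-survey effects and selective return.
- *The HEDIS and medical-record outcomes are affected.* This point concerns the patient survey only.

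**Conclusion.** The point holds as an omission in the survey model. The data to measure within-person change will be collected, but the plan assures only a descriptive account of it. That conclusion rests on the text alone and needs no assumed number. The sizes are conditional. The precision forgone by leaving out baseline (SE multiplier 0.92 to 0.80) assumes ρ of 0.4 to 0.6, a linear scale and a factor unrelated to baseline. The understatement under pooling (1.34 to 1.48) assumes the same ρ, complete answers and an analysis that the plan does not state. The change should be made. It is cheap, and best settled before the survey data are analysed.

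**What to change.** In Data Analysis & Statistical Considerations, specify for the patient survey:

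1. **Change.** One ordinal mixed model with visit (0, 3, 12 months) as a factor and a participant random intercept, added to the planned clinic, provider and state terms. The participant term is needed whatever the practice-level design effect turns out to be. Report the 3-month and 12-month contrasts with baseline, and state the missing-at-random assumption behind using all available answers.
2. **Interpretation.** State that these contrasts are uncontrolled pre-post changes and cannot by themselves be attributed to the intervention.
3. **Associations with participant factors.** Model the 3-month and the 12-month answers separately, each adjusted for the same item at baseline, with the same clinic, provider and state terms. State that this is a different estimand from the change in item 1.
4. **Multiplicity and selection.** Take the p-values for the stepwise and false discovery rate steps from these models.

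The cost is added text, a somewhat more complex model and an explicit missing-data assumption. No new data are needed, since all three surveys are already planned.

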Resulting outcomes data, including all referrals, diagnoses, laboratory and genetic test results, medical procedures, office and ER visits, hospitalizations and medications that occur will be abstracted from patient medical record files prior to patient enrollment and throughout the study period by the participating clinics after patient participation has been concluded at each site and provided to the Duke statistical analysis team with only the patient's unique ID number.

Selection of Subjects –

Population: Study subjects will be comprised of providers and patients at the diverse clinics within in each of the 5 organizations (Duke University, Medical College of Wisconsin, Essentia Health, University of North Texas Health Science Center, and the Air Force).

Providers: all providers in the participating clinics will be selected to be included in the study. We anticipate 100% participation, for an expected enrollment of 365 providers.

ORCA survey participants will be providers, nurses, and administrators at participating clinics at each institution which are involved in MeTree implementation.

Key informants will be providers, nurses, and schedulers at each participating clinic which is involved in MeTree implementation.

Patients: All adult English or Spanish speaking patients scheduled for non-acute visits within 2 weeks will be invited to enroll when they schedule an appointment with their physician. Since this proposal focuses upon prevention and not disease management strategies, those with a study disease (breast, or colon cancer, hereditary cancer syndromes, or CHD) will not be excluded from enrollment but will be excluded from analyses relevant to their disease. We anticipate enrolling 7000 participants at a minimum (to achieve significance for effectiveness measures), but as an observational study will continue to enroll as many as are interested in order to maximize our ability to assess differences across settings, populations, and sociodemographic factors. To reach this goal we need to enroll ~300 participants from each intervention clinic (assumes 10 of the 34 clinics will be dedicated controls). Assuming 20% enrollment (from MeTree™ pilot -see preliminary data), we anticipate being able to enroll at least 9,100 participants.

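### Stepwise p<0.1 is said to identify significant factors and interactions, a rule that does not hold the 5% false discovery rate set just before it

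*Combined protocol and SAP*

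**What the plan says.** Two rules stand close together in Data Analysis & Statistical Considerations, and both use the word *significant*.

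- For the ordinal survey models, with multiplicity as the thing to be corrected: "Associations will be considered significant when the regression coefficient is not zero; a false discovery rate of 5% will be used to correct".
- One sentence later, once adjustment by clinic and by provider has been mentioned, comes the second rule: "A p-value of <0.1 in stepwise regression will identify significant factors such as demographics, intent to change, and their interactions".

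The section then extends the approach: "The analyses for the multiple outcomes will follow the same procedure as the survey outcomes", this time with logistic regression and seven covariate factors that are said to be given in a sample size section. That section is not in the supplied text, and its absence is not counted against the plan.

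The supplied text does not say whether a term found by the stepwise search must also meet the FDR, which tests the FDR covers, or which interactions are searched.

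**The concern.** A 5% FDR limits the expected share of false findings among those declared. A stepwise threshold of p<0.1 has no such property: the share depends on how many terms are searched and how many are real. If the stepwise sentence is followed as written, a demographic factor or an interaction can be reported as significant with no FDR control behind it. An analyst who tries to honour both sentences might run the search first and correct only what remains. That also fails, because the survivors were chosen for their small p-values.

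Findings about factors are a stated use of the data. Selection of Subjects says that enrolment will go past the minimum to "maximize our ability to assess differences across settings, populations, and sociodemographic factors". A reader of the results could not tell whether a significant factor has the 5% FDR behind it or only p<0.1 after a search.

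**Working it through.** The plan gives no computed figure on this point, so there is none to reproduce. The check asks how far apart the rules can be.

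**Inputs from the plan.** FDR 5%; stepwise threshold 0.1; seven covariate factors (named for the logistic models only); and, from Selection of Subjects, "We anticipate enrolling 7000 participants at a minimum".

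**Assumed, because the supplied text does not give them.** A pool of 7 terms, or of 28 (7 plus all 7×6/2 = 21 two-way interactions); independent terms; real slopes of 0.05 SD; all 7000 analysed; a linear model standing in for the ordinal and logistic models; Benjamini-Hochberg (BH) as the FDR procedure.

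**By hand, 28 terms with 3 real.**

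1. *Detection of real terms.* z = 0.05 × √7000 = 4.18. The chance of p<0.1 is Φ(4.18 − 1.645) = Φ(2.54) ≈ 0.994, so nearly all three are found.
2. *Stepwise p<0.1.* The 25 null terms give V ~ Binomial(25, 0.1) false findings, 25 × 0.1 = 2.5 on average. With the three real terms found, FDR = E[V/(V+3)] ≈ 0.41.
3. *BH on survivors only.* A surviving null p-value is spread evenly over 0 to 0.1. Dividing by 0.1 puts it on 0 to 1, so BH at 0.05 on survivors acts as BH at 0.05/0.1 = 0.5. The FDR is half the stepwise value: 0.5 × 0.41 ≈ 0.205.
4. *BH on the full set.* 0.05 × 25/28 ≈ 0.045.

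**Simulation** (forward selection with backward removal at p<0.1; 2000 runs for 7 terms, 800 for 28; n=7000, slope 0.05 SD). FDR is the mean of false findings divided by all findings, counted as zero if nothing is declared.

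| Terms, real | Stepwise p<0.1 | BH on survivors | BH on full set |
|---|---|---|---|
| 28, 3 | 0.410 | 0.205 | 0.042 |
| 28, 7 | 0.216 | 0.106 | 0.036 |
| 28, 14 | 0.090 | 0.044 | 0.026 |
| 28, 20 | 0.036 | 0.018 | 0.013 |
| 7, 3 | 0.094 | 0.046 | 0.027 |
| 7, 5 | 0.032 | 0.016 | 0.013 |

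The first row agrees with the hand calculation. BH on survivors exceeds 5% once the stepwise FDR passes about 10%. With no real terms at all, the chance of a false finding under p<0.1 is 1 − 0.9^7 = 0.522 or 1 − 0.9^28 = 0.948. That is a limiting case and not a forecast.

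**Share of real terms found at slope 0.05 SD** (ranges over both pools and all numbers of real terms above):

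| n analysed | Stepwise p<0.1 | BH on full set |
|---|---|---|
| 7000 | 0.994–0.995 | 0.922–0.982 |
| 3500 | 0.901–0.912 | 0.490–0.789 |
| 2000 | 0.715–0.726 | 0.220–0.463 |

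**The case against.** The best defence is the local context. The FDR sentence speaks of associations. The stepwise sentence follows one on controlling for clinic and provider, and precedes one on a model with fixed covariate factors. In that position p<0.1 can be read as an ordinary threshold for keeping covariates, with *significant* used loosely. This reading is plausible and it removes the conflict. It is not stated, however, and it sits uneasily with a sentence that says the search identifies significant factors and interactions.

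Three stronger conclusions might be inferred, and the documents support none of them.

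- *That the FDR will be ignored.* The text leaves the relation between the two rules open; it does not say that stepwise findings escape the correction. The absent sample size section might also bear on this, so the point is limited to the supplied text.
- *That about 41% of this study's factor findings will be false.* The pool sizes, the numbers of real terms and the slopes are assumed. The pool of 7 is borrowed from the logistic models, where it is unclear whether those factors are searched at all. With most candidates real, p<0.1 gives 3–4%.
- *That the effectiveness result is compromised.* The sentence concerns patient factors and their interactions, not whether the intervention changes outcomes.

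It can also be said that defining significance by a coefficient that is not zero is understandable, since the FDR clause follows directly. That is fair. Still, an estimated coefficient is almost never exactly zero, so an explicit threshold is better.

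**Conclusion.** The point holds as an unresolved wording with a real consequence for factor and interaction claims. Read literally, the stepwise rule does not hold the stated 5% FDR, and correcting only the survivors does not guarantee it either. Under the illustrative assumptions (28 independent candidates, 3 real, slope 0.05 SD, n=7000) the three procedures give about 41%, 21% and 4%. The gap narrows as the share of real candidates rises, and p<0.1 falls below 5% at 5 real of 7 or 20 real of 28. These figures show that the rules are not interchangeable; they do not estimate an error rate for this study. If the sponsor means p<0.1 only for retaining covariates, the point is settled by saying so.

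**What to change.** Replace the stepwise sentence with wording to this effect: *Stepwise selection at p<0.1 is used only to choose adjustment covariates or for exploratory description, and supports no claim of significance. Any factor or interaction to be called significant comes from a candidate set listed before analysis, with the 5% FDR applied to the whole set; significance means an FDR-adjusted p-value below 0.05.* The last clause also replaces the definition by a non-zero coefficient.

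Two clarifications would help but are secondary: whether the FDR family is per outcome or across outcomes (the sponsor's choice), and whether the seven covariates in the logistic models are fixed or searched.

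The drafting cost is a few sentences and a list of terms. The statistical cost is fewer factors declared. At n=7000 and slope 0.05 SD, about 92–98% of real factors are found, against 99% with p<0.1. If far fewer patients are analysed the loss is substantial: at n=2000, about 22–46% against about 72%. A short candidate list, or labelling the remaining terms exploratory, limits this.

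### Logistic regression is the only model assigned to the EMR-type outcomes, although these include laboratory results and visits; numeric ones would have to be dichotomised, with no cut-points given

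*Combined protocol and SAP*

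**What the plan says.** Under Data Analysis & Statistical Considerations, survey outcomes get an ordinal regression. A further group, called only the multiple outcomes, follows the same procedure, "but using a logistic regression model that includes the 7 covariate factors". The seven covariates are not listed; the sentence refers to a sample size section that is not in the available text.

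For clustering, the plan computes a design effect: "if it is 1 we will use standard tests and generalized linear mixed models with clinic and state as random effects". Otherwise it adjusts confidence intervals by conditional logistic regression. The mixed models are given no family or link.

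The outcomes are described elsewhere. Purpose of the Study names HEDIS "measures as intermediate clinical effectiveness measures for CHD and the selected cancers", together with survey and EMR data. The end of Design & Procedures describes the abstracted record as "Resulting outcomes data, including all referrals, diagnoses, laboratory and genetic test results, medical procedures, office and ER visits, hospitalizations and medications", taken from before enrolment and through the study.

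Continuous outcomes are mentioned once: the ordinal model "will fit ordinal survey outcomes to the continuous outcome variables". No model is given in which a continuous variable is clearly the response. No linear or count model, scale for an EMR outcome, cut-point or dichotomisation rule is stated.

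**The concern.** The ordinal model for surveys is set against a logistic model for the other outcomes, so ordinary binary logistic regression is the natural reading. That suits referrals, screening and HEDIS measures met or not met. It does not suit a laboratory value or a number of visits, which it can take only after recoding to yes/no. The fallback, conditional logistic regression, has the same limit.

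At stake is precision on any numeric outcome. There is also an unfilled choice: where recoding is needed and no cut-point is written down, the result depends on a decision that the plan leaves open.

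**Working it through.** **Inputs.** The plan states no power, effect size, standard deviation, ICC, visit rate or laboratory distribution, so it has no figure of its own to reproduce here. The one usable number is about 300 patients per intervention clinic: (34 − 10) × 300 = 7,200, in line with the minimum of 7,000. Everything else below is an assumed range.

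**1. Normal laboratory value, patient-level contrast, small shift.** With a proportion q above the cut, the efficiency of yes/no against continuous analysis is φ(z)² / [q(1 − q)].

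| q above cut | Efficiency | Loss |
|---|---|---|
| 0.5 | 0.637 | 36.3% |
| 0.3 | 0.576 | 42.4% |
| 0.2 | 0.490 | 51.0% |
| 0.1 | 0.342 | 65.8% |

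The median split is the best case (2/π = 0.637), so 36% is a floor for normal values. Cross-check at an assumed standardised difference of 0.1, two-sided 0.05 and 80% power: 1,570 per arm continuous against 2,467 per arm median-split, a ratio of 0.636.

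For other shapes, median split against mean has efficiency 4 f(0)² × variance. This is π²/12 = 0.82 for a logistic distribution (18% loss) and 2 for a Laplace distribution (a gain). The floor therefore needs approximate normality.

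**2. Same value, clinic-level contrast.** Let r be the ICC on the continuous scale and m = 300 in every clinic. Clinic-to-clinic variance enters both analyses, so

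efficiency = [r + (1 − r)/m] / [r + (q(1 − q)/φ(z)² − r)/m].

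Median split at r = 0.01:
- numerator: 0.01 + 0.99/300 = 0.01330
- denominator: 0.01 + (1.5708 − 0.01)/300 = 0.01520
- ratio 0.875, loss 12.5%

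| Assumed ICC | Loss, q = 0.5 | Loss, q = 0.2 | Loss, q = 0.1 |
|---|---|---|---|
| 0 | 36% | 51% | 66% |
| 0.01 | 12.5% | 21% | 33% |
| 0.02 | 8% | 13% | 22% |
| 0.05 | 3.5% | 6% | 11% |

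At a median split the loss drops below one third once the ICC exceeds about 0.0005.

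**3. Visits scored any/none, patient-level contrast.** For a Poisson count with mean μ, the efficiency for the log rate is μ / (e^μ − 1).

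| Assumed mean | Efficiency | Loss |
|---|---|---|
| 0.1 | 0.951 | 4.9% |
| 0.5 | 0.771 | 22.9% |
| 1 | 0.582 | 41.8% |
| 2 | 0.313 | 68.7% |

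The loss passes one third only above a mean of about 0.76, where 53% of patients have at least one visit.

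With overdispersion (negative binomial, size k), P₀ = (k/(k + μ))^k, and the efficiency is {[μ(k/(k + μ))^(k+1)]² / [P₀(1 − P₀)]} / [μ/(1 + μ/k)]. For k from 0.5 to 2 the loss is 7–13% at mean 0.1, 29–40% at mean 0.5 and about 67–68% at mean 2.

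**The case against.** The strongest reply is that the text does not commit the trial to dichotomising anything. The phrase for the further outcomes is undefined, the section it points to is not available, and the Design & Procedures list says what will be abstracted, not what the endpoints are. The list names visits and hospitalisations, not their numbers. Specific CHD laboratory markers such as LDL appear only in Appendix A, for data release. The named effectiveness measures are HEDIS measures, which can be yes/no. Generalized linear mixed models are also named, and these can handle continuous and count data.

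Much of this stands. A reader might infer that every non-survey outcome must be cut into yes/no; the documents do not say so. But they do call the abstracted record outcomes data and name EMR data alongside the HEDIS measures. The mixed models have no stated family, are tied to one branch of the design-effect rule, and give way to a logistic method in the other.

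A second reply is that the design is described as cluster randomised, so a loss computed for independent patients overstates the cost of any clinic-level comparison. That is correct, as step 2 shows. The patient-level figures still apply to within-clinic contrasts, or if the ICC is near zero. The plan itself calls clustering unlikely.

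Four further inferences are tempting but not supported:
- **Over a third lost across the board.** This fails for infrequent visits, for clinic-level contrasts and for some non-normal values.
- **Power falling from 80% to 61%, or 7,000 patients behaving like about 4,460.** Both follow from an efficiency of 0.637 (7,000 × 0.637), but the plan states no power. It also excludes patients with a study disease from analyses of that disease, so 7,000 is not the analysed number for a CHD marker.
- **Cut-points chosen after seeing the data.** The plan leaves room for this but does not announce it.
- **A damaged cost-effectiveness analysis.** Nothing says that it would use a logistic model for visits; it could use the abstracted counts.

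**Conclusion.** The point holds as a gap in the match between outcomes and models. Logistic regression, ordinary or conditional, is the only model tied to the further outcomes. Those outcomes can include numeric laboratory values and visit counts, and neither scales nor cut-points are given. This conclusion rests on reading the model as binary logistic, which the contrast with the ordinal survey model favours.

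If numeric outcomes are analysed as written, the size depends on the case:
- **Roughly normal laboratory value, patient-level contrast:** at least 36% of the information.
- **Same value, clinic-level contrast, 300 per clinic:** for a median split, about 12.5% at an ICC of 0.01 and 8% at 0.02.
- **Visits scored any/none, patient-level contrast:** about 5% to 69% over Poisson means of 0.1 to 2.

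The ICCs, visit means and distributions are assumptions. Outcomes that are yes/no by nature lose nothing.

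**What to change.** In Data Analysis & Statistical Considerations, list each EMR outcome with its scale and model:

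- **Yes/no outcomes** (screening done, referral made, HEDIS measure met): keep logistic mixed models.
- **Numeric laboratory values:** linear mixed models adjusted for the pre-enrolment value, which the planned abstraction already covers; state how patients without one are handled.
- **Visit and admission counts:** negative binomial mixed models with a log observation-time offset.
- **Laboratory measures that are yes/no by intent:** state and justify the cut-point before the data are seen.

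The cost is a change of wording and the use of standard software, with no new data collection. The small downside is that effects are reported on more than one scale: odds ratios, mean differences and rate ratios.
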